8.4.2. Study Endpoints

Primary Endpoint:

The difference in RR between the treatment arms will be calculated at 12 weeks post treatment start in the ITT population. This will be presented using the percentage of patients, including 95% confidence intervals, who achieve CR or PR according to the RECIST v1.1 criteria in each treatment group. Analysis of the primary endpoint will be carried out when all patients have completed treatment and 12 week follow-up assessments.

Secondary Endpoints:

- To determine RR at 6 months post treatment start. This is defined as the percentage of patients achieving confirmed PR or CR as per RECIST v1.1 in the ITT population.
- To measure individual lesion response assessment every 12 weeks taking account of within patient data. Individual lesion response for each patient will be measured over time by assessing PR, CR or SD as per RECIST v1.1 at each time point.
- Toxicity will be graded according to CTCAE version 4.0 and LENT SOMA radiation toxicity grading system after 12 weeks of treatment.
- PFS will be calculated at 1, 2 and 3 years from treatment start until PD or death from any cause.

Patients alive and progression free will be censored at 1, 2 and 3 years, and those patients who are lost to follow-up, withdrawn from follow-up will be censored at the date of last assessment whichever is sooner, respectively.

- OS will be calculated from treatment start until date of death from any cause. Patients, in whom no death is recorded, will be censored at the date they were last seen alive.

Exploratory Endpoints:

Peripheral blood analysis

Peripheral blood collected from patients at baseline, during and follow-up of treatment will be analysed to assess immune function in response to pembrolizumab ± radiotherapy. Assays to examine innate and/or adaptive immune functional response may include, for example, immunophenotyping, cytokine/chemokine arrays. For details, refer to the associated Trial Manual.

Tumour Biopsy samples

Tumour biopsy tissue collected from patients at baseline & during treatment will be examined to assess the tumour microenvironment in response to therapy. Tumour may be used in, for example, multi-colour immunohistochemistry and RNA sequence analysis to investigate TIL infiltration & expression of known tumour-associated antigens. For details, refer to the associated Trial Manual.

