Tumour Imaging	✕									✕ ³		✕ ⁴		
Targeted Physical Exam		✕			✕			✕	✕	✕	✕	✕	✕	
PEMBROLIZUMAB		✕			✕			✕	✕	✕	✕			
RADIOOTHERAPY		← Over 3 days ✕ ⁶ →												
Tumour Biopsies/Archival Tissue Collection/Correlative Studies Blood:														
Archival Tumour Collection (MANDATORY)	✕													
Diagnostic Metast’c Biopsy (MANDATORY)	✕													
Tissue Biopsy (OPTIONAL)					✕									
Research Blood Samples (OPTIONAL)		✕			✕			✕	✕	✕	✕ ⁸			

1. Cycles to be extended past cycle 5 for as long as applicable.
 
2. First 3/6 randomised to Pembrolizumab and Radiotherapy arm only.
 
3. Tumour imaging to be done every 12 weeks from the date of the 1st dose irrespective of delays in treatment cycles. Can be up to 7 days before visit to ensure results at the visit.
 
4. Only if no RECIST assessment has been completed in the last 6 weeks.
 
5. If the participant has been randomised to receive radiotherapy.
 
6. For participants randomised to radiotherapy this should be administered between the 1st and 2nd dose of pembrolizumab i.e. 24Gy in 3 fractions over 3 consecutive days
 
7. End of treatment visit assessments are only applicable if the participant comes off treatment between cycles.
 
8. A follow-up OPTIONAL Research Blood Sample can be taken at either time of response or progression (to be determined by treating clinician)
														

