5.3.8. Tumour Imaging and Assessment of Disease

Tumour response assessments will be carried out by physical examination, and tumour imaging by CT scan and/or MRI. CT scans are the preferred modality for measureable disease unless a participant has a clinical condition e.g. severe contrast allergy, or the lesions are significantly better visualized through the use of an MRI. Tumour response will be assessed based on RECIST v1.1. (See Appendix 4) Baseline lesions must be selected before the start of the treatment. Tumour assessments by CT scan or MRI must be done at 12 weeks, and then 12 weekly thereafter until the end of treatment, progression or withdrawal of the study for any cause. RECIST scans can be performed up to and including 7 days before the participant is due for their next visit to allow the assessment of the scan to be available at the visit.

If no imaging/measurement of the lesion is completed at the requested time point, then the participant cannot be evaluated for progression. If only a subset of the lesions are measured, then this is also considered not evaluable, unless a convincing argument can be made that the contribution of the individual missing lesion(s) would not have changed the assigned time-point response.

Progression of disease should be verified by RECIST 1.1. In cases where progression is equivocal the participant should be re-imaged in 6 weeks. If repeat CT scans or MRI confirm PD, then progression should be declared using the date of the initial scan. If repeat scans do not confirm PD, then the participant is considered not to have progressive disease per RECIST v1.1 and the participant will return to the original imaging schedule. Confirmation of response is not required in these scans. Participants are allowed to continue on treatment beyond progression if there is clinical benefit at investigator's criteria.

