6.9. Survival Follow-up

Once a participant experiences confirmed disease progression or starts a new anti-cancer therapy, the participant moves into the survival follow-up phase. Participants will not be expected to attend clinic visits during the survival follow-up but information on the participant's status will be gathered by the research team from the participant's medical notes, the participant's GP and telephoning the patients directly is applicable. The survival period will continue every 12 weeks for 3 years until death, lost to follow up, withdrawal of consent or the end of the study.

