8.5. Planned method of analysis

Continuous data will be summarised using means, standard deviations, medians, minimum and maximum values and where appropriate 95% confidence intervals. Nominal and ordinal categorical data will be summarised using the number of observations and percentages. All significance tests will be two-sided using an overall alpha level of 5%. It is anticipated that adjustment will be made for repeated significance testing using a Bonferroni correction specifically for all secondary endpoints.

Primary Endpoint:

- The RR 12 weeks post treatment will be summarized as the percentage (including 95% confidence intervals) of responders and will be compared between treatment arms using the chi-squared test for proportions.

Secondary Endpoints:

- The RR at 6 months will be summarized as a percentage (including 95% confidence intervals) of responders and will be compared between treatment arms using the chi-squared test for proportions.

- To measure individual lesion response assessment every 12 weeks within each patient using McNemar's test of paired proportions between time points.
- The proportion of patients experiencing grade 3-5 toxicity will be compared on a regimen basis using the chi-squared test. Fishers exact test will be used when expected cell frequencies are <5.
- PFS and OS at 1, 2 and 3 years, respectively, will be calculated using Kaplan-Meier methods. Median PFS and OS with associated 95% confidence intervals will be presented by treatment and compared using the log rank test. Cox Proportional hazards regression model analysis will be used to calculate the hazard ratio between treatments along with its 95% confidence intervals and will be adjusted for other identified prognostic factors in a multivariate setting.

Exploratory Endpoints:

- Continuous exploratory data will be summarised using means, standard deviations, medians, minimum and maximum values attaching 95% confidence intervals where appropriate. Categorical data will be summarised using frequencies and proportions, attaching confidence intervals where necessary.

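### The PFS rule carries patients who stop pembrolizumab without progression to the 1-, 2- and 3-year landmarks unscanned, which biases PFS upward under this protocol's imaging schedule

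*Combined protocol and SAP*

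**What the plan says.** **Censoring (8.4.2).** The endpoint is defined by "PFS will be calculated at 1, 2 and 3 years from treatment start until PD or death from any cause". One branch of the censoring sentence reads "Patients alive and progression free will be censored at 1, 2 and 3 years". The other reads "those patients who are lost to follow-up, withdrawn from follow-up will be censored at the date of last assessment whichever is sooner, respectively". Neither mentions a tumour assessment.

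**Method (8.5).** "PFS and OS at 1, 2 and 3 years, respectively, will be calculated using Kaplan-Meier methods", with a log-rank test and a Cox model between arms.

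**Imaging (5.3.8 and the schedule table in 5.1).** Scans are at 12 weeks and then "12 weekly thereafter until the end of treatment, progression or withdrawal of the study for any cause". The end-of-treatment scan carries the footnote "Only if no RECIST assessment has been completed in the last 6 weeks". The table marks no imaging in the safety or survival follow-up columns. Section 5.3.8 also says that a participant not imaged at a time point cannot be evaluated for progression.

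**After stopping (3.4, 5.1, 5.2.5, 6.9).** Patients have a 30-day safety visit and then 12-weekly survival follow-up from notes, the GP or telephone: "Participants will not be expected to attend clinic visits during the survival follow-up". The survival contact records status, anti-cancer treatment, and death or loss.

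**Stopping without progression.** Section 6.11 allows it after complete response or 24 months of treatment, and 6.3.8 and 6.10.1 require or allow it for toxicity. Section 6.11 defines study withdrawal as stopping both the drug and future assessments, so stopping the drug alone is not withdrawal.

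**The concern.** Take a patient last scanned at month 5 who stops for toxicity and is known from the GP to be alive at month 24. This patient is neither lost nor withdrawn and has no recorded progression. The natural reading of 8.4.2 censors the patient at the 2-year landmark, with some 19 months of progression-free time and no tumour assessment. Death would count as an event; progression in that interval has no planned means of detection. The analysis rule thus credits time that 5.3.8 treats as not evaluable.

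The second branch has a related gap. Section 5.2.5 also calls the survival contact an assessment, so a lost or withdrawn patient could be censored at a contact without a scan.

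At stake are the landmark PFS rates and the PFS comparison. Adding radiotherapy could plausibly change how often patients stop for complete response or toxicity. An arm that stops more often would then gain apparent PFS.

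**Working it through.** The plan states no expected PFS rate, event count or PFS power, so it has no figure of its own to reproduce. What follows illustrates size.

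**Inputs**
- Median PFS 7 months, exponential. Section 1.2.2 says only that the median in an earlier cohort exceeded 7 months. λ = ln 2/7 = 0.0990 per month.
- Median post-progression survival 12 months (assumption). μ = ln 2/12 = 0.0578 per month.
- Scans every 12 weeks (5.3.8), that is 84/30.44 = 2.76 months. The last scans before 12, 24 and 36 months fall at 11.04, 22.08 and 35.88 months.
- A fraction f of those progression-free at month 6 stops then (assumption, 10–30%). No later progression is found in these patients.

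**Step 1: PFS if scanning had continued.** S = 0.5^(scan time/7) = 33.5%, 11.2% and 2.9% at 1, 2 and 3 years. This scan-detected curve is the right comparator. The exact progression-free proportion at 12 months is 0.5^(12/7) = 30.5%, but any 12-weekly scan schedule detects progression late.

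**Step 2: stoppers under the written rule.** They remain event-free until death. The probability of being alive u months after month 6 is G(u) = (λe^(−μu) − μe^(−λu))/(λ − μ), so G(6) = 0.924, G(18) = 0.613 and G(30) = 0.352. Multiplying by P(progression-free at 6 months) = 0.5^(6/7) = 0.552 gives W = 51.0%, 33.8% and 19.5%.

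**Step 3: overstatement = f × (W − S), in percentage points**

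| f | 1 year (f × 17.5) | 2 years (f × 22.6) | 3 years (f × 16.6) |
|---|---|---|---|
| 10% | 1.8 | 2.3 | 1.7 |
| 20% | 3.5 | 4.5 | 3.3 |
| 30% | 5.3 | 6.8 | 5.0 |

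At f = 20% the written rule gives 37.0%, 15.8% and 6.2%. A simulation of 400,000 patients gave the same three values.

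**Step 4: stoppers who progress more slowly.** With one third of the hazard after month 6, the same formulas give W = 53.6%, 45.1% and 34.8%, against 46.7%, 32.5% and 20.6% had these patients been scanned. The differences are 6.9, 12.6 and 14.2. At f = 20% the overstatement is 1.4, 2.5 and 2.8 points; at f = 10% it is 0.7, 1.3 and 1.4.

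**Step 5: progression found from notes.** If half of the later progressions are found and correctly dated, 3.5 points at 1 year becomes 3.5 × 0.5 = 1.8. At 80% found it becomes 3.5 × 0.2 = 0.7.

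**Step 6: between-arm effect.** A separate simulation gave both arms identical true PFS (median 7 months, post-progression survival 12 months, all drug stopped by 24 months). With 10% against 30% stopping per year, the hazard ratio was 0.89 in favour of the arm that stops more under the written rule, and 1.04 with censoring at the last scan. With 10% in both arms the values were 1.00 and 0.99.

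**The case against.** **The sentence can be read differently.** It might mean truncation at each horizon, with earlier censoring at the last assessment for anyone not seen. Since 5.3.8 calls an unscanned patient not evaluable, such a patient might not count as progression-free at all. This is a fair reading, but the last-assessment clause is attached grammatically to lost and withdrawn patients. Even on the kinder reading, the rule is undefined for patients who stop drug and stay in survival follow-up.

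**A reader might infer that the censoring date is wrong whatever the imaging schedule.** The documents do not support that. If scans continued to progression, landmark censoring would be ordinary administrative censoring and harmless. The bias arises because this protocol ends scans with treatment.

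**A reader might infer that later progressions are always missed.** That is also too strong. Notes and GP records are consulted and anti-cancer treatments recorded, so some could surface. No section requires progression to be captured there, and 5.3.8 wants it verified by RECIST.

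**Censoring at the last scan has its own error.** This stands. If all stoppers are censored at their last scan, Kaplan-Meier recovers the curve of those who did not stop. With stoppers at one third of the hazard and f = 20%, it understates PFS by 0.2 × (46.7 − 33.5) = 2.6 points at 1 year and 0.2 × (32.5 − 11.2) = 4.3 at 2 years. Both exceed the written rule's overstatement in Step 4.

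**PFS is secondary.** This is true. The 12-week response rate and OS are untouched, and 8.6 lets the handling of secondary variables be updated before the analysis plan is final.

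**Conclusion.** The concern holds for one group: patients who stop pembrolizumab without progression and remain in survival follow-up. A smaller gap concerns lost or withdrawn patients, whose last assessment need not be a scan. For the first group the written rule biases PFS upward to the extent that later progression goes unrecorded. The comparison is exposed if stopping without progression differs by arm.

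Across the cases in Steps 3 and 4 the overstatement is roughly 1 to 5 points at 1 year and 1 to 7 at 2 years. This rests on assumed stopping at a single time, exponential PFS and 12-month post-progression survival. It is smaller still if progression surfaces through notes. The hazard ratio of 0.89 belongs to one assumed scenario. None of these figures predicts the trial's actual bias, because the documents give no stopping rate. The matter should be corrected before analysis but does not threaten the primary result.

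**What to change.** Replace the PFS censoring sentence in 8.4.2 with rules to this effect:

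1. Censor patients without progression or death at their last evaluable RECIST tumour assessment, or at time zero if there is none. Do not use clinic-visit or survival-contact dates.
2. Count a death as a PFS event only within a pre-stated window of the last evaluable assessment, for example two scheduled scan intervals (24 weeks). Otherwise censor at that assessment. Without this rule, stoppers who die late stay in the risk set until death while surviving stoppers are censored back. In the 20% scenario that gave 35.4%, 12.7% and 2.5%, against scan-detected 33.4%, 11.2% and 2.9%.
3. Read the 1-, 2- and 3-year rates from the Kaplan-Meier curve and report numbers at risk.
4. Add a sensitivity analysis that counts all deaths, and any progression recorded in notes, as events.

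**Cost.** This is SAP wording only. Reported PFS at 1 and 2 years will probably be slightly lower and intervals wider. Censoring will be informative if stoppers have a better prognosis, which is why item 4 is needed.

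Wording cannot supply missing scans. If most patients stop by 24 months, the curve is nearly flat from 24 to 36 months. In one simulated case (all stopped by 24 months, 5% stopping per year before that, median PFS 7 months, post-progression survival 6 months), last-scan censoring gave 9.1% at 3 years, the written rule 6.1% and the truth was 2.8%. Three-year PFS should carry that caution under either rule.

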8.5. Planned method of analysis

Continuous data will be summarised using means, standard deviations, medians, minimum and maximum values and where appropriate 95% confidence intervals. Nominal and ordinal categorical data will be summarised using the number of observations and percentages. All significance tests will be two-sided using an overall alpha level of 5%. It is anticipated that adjustment will be made for repeated significance testing using a Bonferroni correction specifically for all secondary endpoints.

Primary Endpoint:

- The RR 12 weeks post treatment will be summarized as the percentage (including 95% confidence intervals) of responders and will be compared between treatment arms using the chi-squared test for proportions.

Secondary Endpoints:

- The RR at 6 months will be summarized as a percentage (including 95% confidence intervals) of responders and will be compared between treatment arms using the chi-squared test for proportions.

- To measure individual lesion response assessment every 12 weeks within each patient using McNemar's test of paired proportions between time points.
- The proportion of patients experiencing grade 3-5 toxicity will be compared on a regimen basis using the chi-squared test. Fishers exact test will be used when expected cell frequencies are <5.
- PFS and OS at 1, 2 and 3 years, respectively, will be calculated using Kaplan-Meier methods. Median PFS and OS with associated 95% confidence intervals will be presented by treatment and compared using the log rank test. Cox Proportional hazards regression model analysis will be used to calculate the hazard ratio between treatments along with its 95% confidence intervals and will be adjusted for other identified prognostic factors in a multivariate setting.

Exploratory Endpoints:

- Continuous exploratory data will be summarised using means, standard deviations, medians, minimum and maximum values attaching 95% confidence intervals where appropriate. Categorical data will be summarised using frequencies and proportions, attaching confidence intervals where necessary.

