2.1.2 Secondary Objectives

Objectives:

- To evaluate response rates by RECIST v1.1 post treatment
- To evaluate response in non-irradiated lesions
- To assess the efficacy of pembrolizumab based on Progression Free Survival (PFS).
- To assess the efficacy of pembrolizumab based on Overall Survival (OS).
- To assess the safety and tolerability of pembrolizumab alone and in combination with high dose radiotherapy.

Hypothesis: High dose radiotherapy results in immunogenic cell death resulting in release of antigens that stimulate a systemic immune response, converting the irradiated tissue into an *in situ* vaccine.

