2.2.2 Secondary Endpoints

- To determine response rates by RECIST v1.1 at 6 months post treatment
- To measure individual lesion response assessment every 12 weeks taking account of within patient data
- To assess the toxicity of the combination of pembrolizumab and high dose radiotherapy after 12 weeks of treatment.
- To assess PFS at 1, 2 and 3 years post treatment.
- To assess OS in the arms of the study.

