8.2. Sample Size and Power Considerations

The sample size of this study was calculated using a 2-sided α of 5%; power of 80%; RECIST response rate in the pembrolizumab arm is 30%; RECIST response rate in the pembrolizumab and radiotherapy arm is 50%. The study will randomise 234 patients in total (210 minimally required for statistical power calculation purposes, 105 patients in each arm; 20 additional patients to account for potential drop outs – an expected drop out rate of 10%) over 18 months i.e. 11-12 patients per month in approximately 15 to 24 UK centres. In the event that enrolment is slower than expected the Trial Steering Committee will consider adding additional UK sites. Patients enrolled in the trial are expected to be recruited from the routine clinics of the participating centres.

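### The planned Bonferroni correction covers the grade 3-5 toxicity comparison, and no between-arm difference or confidence interval is planned, so a moderate excess of harm becomes materially harder to declare

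*Combined protocol and SAP*

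**What the plan says.** Section 2.1.2 lists as a secondary objective: "To assess the safety and tolerability of pembrolizumab alone and in combination with high dose radiotherapy". Section 2.2.2 makes toxicity one of five secondary endpoints: "To assess the toxicity of the combination of pembrolizumab and high dose radiotherapy after 12 weeks of treatment". The other four are 6-month response rate, individual lesion response, PFS and OS.

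Section 8.5 sets the general level: "All significance tests will be two-sided using an overall alpha level of 5" per cent. It then adds: "It is anticipated that adjustment will be made for repeated significance testing using a Bonferroni correction specifically for all secondary endpoints". It states no number of tests and no exemption for safety.

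The toxicity bullet of the same section reads: "The proportion of patients experiencing grade 3-5 toxicity will be compared on a regimen basis using the chi-squared test". Fisher's exact test replaces the chi-squared test when expected counts are small. Categorical data in general are summarised by counts and percentages. The bullet names no risk difference, confidence interval or margin. By contrast, the response-rate bullets ask for 95% intervals on the percentages, and the PFS/OS bullet asks for a hazard ratio with its interval.

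Under section 8.4.1 safety is analysed by treatment received, in patients given at least one dose.

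**The concern.** A Bonferroni correction protects against false claims of benefit when several efficacy endpoints are tested. Applied to a harm endpoint it works the other way: it raises the evidence needed before an excess of severe toxicity can be declared, and each further efficacy comparison in the family raises it again.

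This matters here because section 6.2.3 acknowledges that the radiotherapy schedule is not an established palliative dose in melanoma, that giving it concurrently with pembrolizumab is not standard care, and that patient safety comes first. The final comparison between arms is the main randomised evidence on added toxicity. If its planned output is two percentages and an adjusted test, a report can state that there was no significant difference without showing how large an excess remains compatible with the data.

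**Working it through.** **Inputs from the documents.** Two-sided 5% level (8.2, 8.5); 80% power for response rates of 30% and 50% (8.2); 105 per arm required and 234 randomised 1:1, so 117 per arm (8.2, 8.3).

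**Assumptions.** The documents give no grade 3-5 rate for pembrolizumab alone and no increase that would matter. I use control rates of 10, 15, 20 and 30%, rises of 10, 15 and 20 points, and 117 treated patients per arm.

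**The plan's own figure.** With p̄ = 0.40,

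n = [1.960·√(2·0.40·0.60) + 0.842·√(0.30·0.70 + 0.50·0.50)]² / 0.20² = 93 per arm.

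The continuity correction gives (93/4)·[1 + √(1 + 4/(93·0.20))]² = 103, close to the stated 105. Allowing for 10% dropout, 210/0.9 = 233.3, rounded up to 234. The sample size is therefore reproduced, and it was set for response rate alone.

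**Level for toxicity.** The five endpoints of section 2.2.2 give 0.05/5 = 0.01. The four secondary bullets of section 8.5, where PFS and OS share one, give 0.05/4 = 0.0125. About ten separate tests would give 0.005.

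**Power formula, worked for 15% v 25%.** With p̄ = 0.20, the standard error under the null is √(2·0.20·0.80/117) = 0.0523. Under the alternative it is √[(0.15·0.85 + 0.25·0.75)/117] = 0.0519.

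- At 0.05: Φ[(0.10 − 1.960·0.0523)/0.0519] = Φ(−0.05) = 48%.
- At 0.01: Φ[(0.10 − 2.576·0.0523)/0.0519] = Φ(−0.67) = 25%.

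Exact enumeration of the uncorrected chi-squared test, counting rejections towards more toxicity with radiotherapy, gives 49% and 26%.

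**Exact power, 117 per arm**

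| Control v combination | α = 0.05 | α = 0.0125 | α = 0.01 |
|---|---|---|---|
| 10 v 20% | 58% | 36% | 34% |
| 15 v 25% | 49% | 28% | 26% |
| 20 v 30% | 42% | 23% | 21% |
| 30 v 40% | 36% | 18% | 17% |
| 10 v 25% | 87% | 71% | 69% |
| 15 v 30% | 79% | 61% | 58% |
| 20 v 35% | 73% | 54% | 50% |
| 30 v 45% | 67% | 45% | 42% |
| 10 v 30% | 98% | 92% | 91% |
| 15 v 35% | 95% | 86% | 85% |
| 20 v 40% | 92% | 81% | 79% |
| 30 v 50% | 89% | 75% | 71% |

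At 0.005 a 10-point rise has power of 25, 18, 15 and 11%. With 105 per arm, 15 v 25% has 44% at 0.05 and 22% at 0.01.

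**Sample size or correction?** Take 80% as the benchmark for a 10-point rise. The shortfall at an uncorrected 0.05 is 22, 31, 38 and 44 points across the four control rates. The correction to 0.01 removes a further 24, 23, 22 and 19 points. Sample size is the larger part for control rates of 15% and above, and the two are about equal at 10%. Reaching 80% power for a 10-point rise, at control rates of 10-20%, would need 199 to 294 per arm at 0.05 and 297 to 437 at 0.01.

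**What an interval would show.** The 95% half-width is 1.96·√[(p₀q₀ + p₁q₁)/117]. It is 9.1 points for 10 v 20% and 12.2 points for 30 v 40%. As an illustration, 18/117 v 34/117 (15.4% v 29.1%) is a difference of 13.7 points with an interval of about 3 to 24 points. Its chi-squared p-value is 0.0119, which fails at 0.01 and passes at 0.0125.

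**The case against.** A reader might infer that toxicity will be judged only by a p-value, and that any real excess will most likely be reported as non-significant. The documents support neither.

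- **Other safety evidence is planned.** Per-arm percentages will be shown and Fisher's test is the fallback. The first three combination patients are seen weekly for six weeks, with three more if toxicity is seen (3.2.1). The first six combination patients are reviewed at 12 weeks (8.5.1, 10.8.1.1). The Trial Steering Committee monitors safety, with a closed session acting as data monitoring committee (8.7, 10.8.2). These stand, but none of them supplies a between-arm estimate with its uncertainty.
- **The size of the rise decides the matter.** At 0.01 a 10-point rise is missed in 66-84% of trials. A 15-point rise is missed in 31-58%, which is about even, and a 20-point rise in only 9-29%. No document says which rise is relevant.
- **Removing the correction is not enough.** A 10-point rise is already missed in 42-64% of trials at 0.05. This is why the estimate and interval matter more than the choice of level.
- **The rule is provisional.** Section 8.5 says only that adjustment is anticipated, and section 8.6 lets methods for secondary variables be updated after data review. It is nevertheless the only multiplicity rule given, and in an open-label trial the exemption is better fixed before comparative data are seen.
- **The contrast with response rate is limited.** The intervals specified there are for each arm's percentage, not explicitly for the difference. This is correct, and only the PFS/OS bullet plans a between-arm estimate with an interval.
- **Counts allow anyone to derive a difference.** They do, but what is not prespecified may not be reported.

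The plan nowhere says that a non-significant toxicity test means safety. The point is that it does not guard against that reading.

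**Conclusion.** The point holds in limited form. As written, the toxicity comparison is inside the Bonferroni family, and no between-arm difference or interval is planned for it. At 117 per arm and control rates of 10-30%, moving from 0.05 to 0.01 costs 19 to 24 percentage points of power for a 10-point rise and 18 to 25 for a 15-point rise. For a 20-point rise it costs about 6 to 18. Using 0.0125 changes little: power for a 10-point rise is 18-36%.

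The correction thus makes a moderate excess materially harder to declare, while the low power for a 10-point rise is mainly a matter of a trial sized for response rate. The figures rest on assumed control rates, assumed rises, an unstated divisor and equal treated groups of 117. This is an improvement that should be made, not a flaw that undermines the trial.

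**What to change.** In section 8.5:

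1. Limit the Bonferroni correction to the secondary efficacy endpoints and exempt the grade 3-5 toxicity comparison. State the number of tests in the same sentence: the four efficacy endpoints of section 2.2.2 would each be tested at 0.05/4 = 0.0125.
2. Report the between-arm difference in grade 3-5 proportions with an unadjusted two-sided 95% confidence interval as the main comparative safety result, beside the per-arm rates.
3. State that a non-significant test will not be taken as evidence of no added toxicity.

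The cost is a few sentences and one interval, with no added patients, visits or data. The downside is a higher false-signal rate for toxicity, 5% instead of about 1% (two-sided), which errs on the cautious side for a safety endpoint.
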